#### 17.6 Unanticipated Problems

Unanticipated problems involving risks to participants or others (UPs) are defined as any incident, experience or outcome that meets all of the following criteria:

- Unanticipated (in terms of nature, severity, or frequency) given (a) the
  research procedures that are described in the protocol-related documents,
  such as the IRB-approved research protocol and informed consent document;
  and (b) the characteristics of the subject population being studied; and
- Related or possibly related to participating in the research (possibly related means there is a reasonable probability that the incident, experience or outcome may have been caused by procedures involved in the research); and
- Suggests that the research place participants or others at a greater risk of harm (including physical, psychological, economic, or social harm) than was previously known or recognized.

Participating sites are responsible for reporting all UPs to MSK as soon as possible but within 3 calendar days of learning of the event. UPs that are SAEs should be reported to MSK via SAE Report form as per section 17.3 of this protocol. All other UPs should be reported to MSK in a memo signed by the site PI.

MSK is responsible for submitting UPs to the MSK IRB/PB according to institutional guidelines. In addition, MSK is responsible for notifying participating sites of all non-SAE UPs that may affect the sites.

#### 18.1 INFORMED CONSENT PROCEDURES

Before protocol-specified procedures are carried out, consenting professionals will explain full details of the protocol and study procedures as well as the risks involved to participants prior to their inclusion in the study. Participants will also be informed that they are free to withdraw from the study at any time. All participants must sign an IRB/PB-approved consent form indicating their consent to participate. This consent form meets the requirements of the Code of Federal Regulations and the Institutional Review Board/Privacy Board of this Center. The consent form will include the following:

- 1. The nature and objectives, potential risks and benefits of the intended study.
- 2. The length of study and the likely follow-up required.
- 3. Alternatives to the proposed study. (This will include available standard and investigational therapies. In addition, patients will be offered an option of supportive care for therapeutic studies.)
- 4. The name of the investigator(s) responsible for the protocol.
- 5. The right of the participant to accept or refuse study interventions/interactions and to withdraw from participation at any time.

Before any protocol-specific procedures can be carried out, the consenting professional will fully explain the aspects of patient privacy concerning research specific information. In addition to signing the IRB Informed Consent, all patients must agree to the Research Authorization component of the informed consent form.

Each participant and consenting professional will sign the consent form. The participant must receive a copy of the signed informed consent form.

#### 18.2 Inform Consent Procedures for Participating Sites

The investigators listed on the Consenting Professionals Lists at each participating site may obtain informed consent and care for the participants according to good clinical practice and protocol guidelines.

A note will be placed in the medical record documenting that informed consent was obtained for this study, and that the participant acknowledges the risk of participation.

#### 20.0 APPENDICES

## Appendix A – Risks of Fetal Exposure, Pregnancy Testing Guidelines and Acceptable **Birth Control Methods**

## **Risks Associated with Pregnancy**

The use of lenalidomide in pregnant females and nursing mothers has not been studied nor has the effect of the lenalidomide on human eggs and sperm. Lenalidomide is structurally related to thalidomide. Thalidomide is a known human teratogenic active substance that causes severe life-threatening birth defects. An embryofetal development study in animals indicates that lenalidomide produced malformations in the offspring of female monkeys who received the drug during pregnancy. The teratogenic effect of lenalidomide in humans cannot be ruled out. Therefore, a risk minimization plan to prevent pregnancy must be observed.

All study participants must be registered into the mandatory Revlimid REMS™, and be willing and able to comply with the requirements of REMS™...

## Criteria for females of childbearing potential (FCBP)

This protocol defines a female of childbearing potential as a sexually mature female who: 1) has not undergone a hysterectomy or bilateral oophorectomy or 2) has not been naturally postmenopausal for at least 24 consecutive months (i.e., has had menses at any time in the preceding 24 consecutive months).

## The investigator must ensure that:

- Females of childbearing potential comply with the conditions for pregnancy risk minimization, including confirmation that she has an adequate level of understanding
- Females NOT of childbearing potential acknowledge that she understands the hazards and necessary precautions associated with the use of lenalidomide
- Male patients taking lenalidomide acknowledge that he understands that traces of lenalidomide have been found in semen, that he understands the potential teratogenic risk if engaged in sexual activity with a female of childbearing potential, and that he understands the need for the use of a condom even if he has had a vasectomy, if engaged in sexual activity with a female of childbearing potential.

## Contraception

Females of childbearing potential (FCBP) enrolled in this protocol must agree to use two reliable forms of contraception simultaneously or to practice complete abstinence from heterosexual intercourse during the following time periods related to this study: 1) for at least 28 days before starting lenalidomide; 2) throughout the entire duration of lenalidomide treatment; 3) during dose interruptions; and 4) for at least 28 days after lenalidomide discontinuation.

Memorial Sloan Kettering Cancer Center IRB Number: 14-179 A(6)
Approval date: 12-Dec-2017

Administrative Update 1:06-Dec-2018

The two methods of reliable contraception must include one highly effective method and one additional effective (barrier) method. FCBP must be referred to a qualified provider of contraceptive methods if needed. The following are examples of highly effective and additional effective methods of contraception:

- Highly effective methods:
  - Intrauterine device (IUD)
  - Hormonal (birth control pills, injections, implants)
  - Tubal ligation
  - Partner"s vasectomy
- Additional effective methods:
  - Male condom
  - Diaphragm
  - Cervical Cap

Because of the increased risk of venous thromboembolism in patients with multiple myeloma taking lenalidomide and dexamethasone, combined oral contraceptive pills are not recommended. If a patient is currently using combined oral contraception the patient should switch to one of the effective method listed above. The risk of venous thromboembolism continues for 4–6 weeks after discontinuing combined oral contraception. The efficacy of contraceptive steroids may be reduced during co-treatment with dexamethasone.

Implants and levonorgestrel-releasing intrauterine systems are associated with an increased risk of infection at the time of insertion and irregular vaginal bleeding. Prophylactic antibiotics should be considered particularly in patients with neutropenia.

## Pregnancy testing

Medically supervised pregnancy tests with a minimum sensitivity of 50 mIU/mL must be performed for females of childbearing potential, including females of childbearing potential who commit to complete abstinence, as outlined below.

#### Before starting lenalidomide

#### Female Patients:

FCBP must have two negative pregnancy tests (sensitivity of at least 50 mIU/mL) prior to prescribing lenalidomide. The first pregnancy test must be performed within 10-14 days prior to prescribing lenalidomide and the second pregnancy test must be performed within 24 hours prior to prescribing lenalidomide. The patient may not receive lenalidomide until the Investigator has verified that the results of these pregnancy tests are negative.

Memorial Sloan Kettering Cancer Center IRB Number: 14-179 A(6)
Approval date: 12-Dec-2017

Administrative Update 1 : 06-Dec-2018

#### Male Patients:

Must agree to practice complete abstinence or agree to use a condom during sexual contact with pregnant females or females of childbearing potential throughout the entire duration of lenalidomide treatment, during dose interruptions and for at least 28 days following lenalidomide discontinuation, even if he has undergone a successful vasectomy.

## During study participation and for 28 days following lenalidomide discontinuation

#### Female Patients:

- FCBP with regular or no menstrual cycles must agree to have pregnancy tests weekly for the first 28 days of lenalidomide treatment, including dose interruptions and then every 28 days throughout the remaining duration of lenalidomide treatment, including dose interruptions, at lenalidomide discontinuation, and at Day 28 following lenalidomide discontinuation. If menstrual cycles are irregular, the pregnancy testing must occur weekly for the first 28 days of lenalidomide treatment, including dose interruptions, and then every 14 days throughout the remaining duration of lenalidomide treatment, including dose interruptions, at lenalidomide discontinuation, and at Day 14 and Day 28 following lenalidomide discontinuation.
- At each visit, the Investigator must confirm with the FCBP that she is continuing to use two reliable methods of birth control at each visit during the time that birth control is required.
- If pregnancy or a positive pregnancy test does occur in a study patient, lenalidomide must be immediately discontinued.
- Pregnancy testing and counseling must be performed if a patient misses her period or if her pregnancy test or her menstrual bleeding is abnormal. Lenalidomide treatment must be temporarily discontinued during this evaluation.
- Females must agree to abstain from breastfeeding during study participation and for at least 28 days after lenalidomide discontinuation.

#### Male Patients:

- Must practice complete abstinence or use a condom during sexual contact with pregnant females or females of childbearing potential throughout the entire duration of lenalidomide treatment, during dose interruptions and for at least 28 days following lenalidomide discontinuation, even if he has undergone a successful vasectomy.
- If pregnancy or a positive pregnancy test does occur in the partner of a male study patient during study participation, the investigator must be notified immediately.

#### Additional precautions

Patients should be instructed never to give lenalidomide to another person.

- Female patients should not donate blood during therapy and for at least 28 days following discontinuation of lenalidomide.
- Male patients should not donate blood, semen or sperm during therapy or for at least
   28 days following discontinuation of lenalidomide.
- Only enough lenalidomide for one cycle of therapy may be prescribed with each cycle of therapy.

## Appendix B - Canadian Cardiovascular Society Angina Classification

#### Class I

Ordinary physical activity, (e.g., walking and climbing stairs) does not cause angina; angina occurs with strenuous, rapid, or prolonged exertion at work or recreation.

#### Class II

Slight limitation of ordinary activity; angina occurs on walking or climbing stairs rapidly; walking uphill; walking or stair climbing after meals, in cold, in wind, or under emotional stress; or only during the few hours after awakening; when walking > 2 blocks on level ground; or when climbing more than 1 flight of stairs at a normal pace and in normal conditions.

#### Class III

Marked limitation of ordinary physical activity; angina occurs on walking 1 to 2 blocks on level ground or climbing 1 flight of stairs at a normal pace in normal conditions.

#### Class IV

Inability to perform any physical activity without discomfort; anginal symptoms may be present at rest.

Campeau L. Grading of angina pectoris. Circulation 1975; 54:522-3.

## Appendix C - New York Heart Association Classification of Cardiac Disease

#### **NYHA Classification of Cardiac Disease**

Class	Functional Capacity	Objective Assessment
I	Patients with cardiac disease but without resulti ng limitations of physical activity. Ordinary physical activity does not cause undue fatigue, palpitation, dyspnea, or anginal pain.	,
II	Patients with cardiac disease resulting in slight limitation of physical acti vity. They are comfortable at rest. Ordinary physical activity results in fatigue, palpitation, dyspnea, or anginal pain.	Objective evidence of minimal cardiovascular disease.
III	Patients with cardiac disease resulting in marked limitation of physical activity. They are comfortable at rest. Less than ordinary activity causes fatigue, palpitation, dyspnea, or anginal pain.	Objective evidence of moderately severe cardiovascular disease.
IV	Patients with cardiac disease resulting in inability to carry on any physical activity without discomfort. Symptoms of heart failure or the anginal syndrome may be present even at rest. If any physical activity is undertaken, discomfort is increased.	

Source: The Criteria Committee of New York Heart Association. Nomenclature and Criteria for Diagnosis of Diseases of the Heart and Great Vessels. 9th Ed. Boston, MA: Little, Brown & Co; 1994:253-256.

# Appendix D – Grading Scales for modified Severity-Weighted Assessment Tool mSWAT

1. Total Body Surface Area (TBSA) Involvement by Skin Disease

The body is divided into 12 regions with pre-assigned %TBSA based on the burn literature. The extent of skin disease in each region is quantified by using the patient"s palm to measure the %TBSA involvement within region: patient"s palm with 4 fingers (excluding the thumb) is 1% of TBSA. Patient"s palm without fingers is 0.5% of TBSA. The patient"s palm with 4 fingers is traced on a transparency sheet at the baseline visit, using a permanent marker that will not rub off or smear. The transparency of the patient"s palm should be used in all mSWAT assessments during the course of the clinical study. The transparency will be labeled with the patient"s study ID number kept in the patient"s study file on site. Using the baseline visit transparency of the patient"s palm, the investigator will measure and record on the electronic case report form (Example of table from eCRF is given below) the %TBSA for each lesion type within each of the 12 regions.

## 2. Severity Weighting Factor

The severity weighting factors will be the following:

1= patch (flat erythema or erythema with mild infiltration)

2=plague (elevated erythema or erythema with moderate infiltration)

4= tumor or ulceration (erythema with fissuring, ulceration or tumor)

Patch is defined as abnormal skin not elevated from normal skin. A

plaque is defined as abnormal skin elevated from normal skin by < 5

mm. A plaque elevated ≥ 5 mm is a tumor.

#### 3. Calculating Skin Scores

The sum of %TBSA by lesion is derived by summing the %TBSA from all regions affected by the lesion. The sum of %TBSA across lesion types (patches, plaques and tumors) within each region cannot exceed the %TBSA for the region. For example, the %TBSA for the head region is 7%. The sum of %TBSA across lesion types from head can only range from 0-7%. The skin score subtotal by lesion type are derived by multiplying the sum of %TBSA for patches from all regions by 1, sum of %TBS of plaques from all regions by 2, and the sum of %TBSA of tumors or ulcers from all regions by 4. The skin score total is derived from summing the skin score subtotals for patches, plaques and tumors or ulcers. The skin score total is dimensionless with a scale of 0 to 400.

Region	% TBSA for the region	% TBSA Patch (or flat erythema)	% TBSA Plaque (or elevated/indurated erythema)	% TBSA Tumor/ Ulceration (or erythema w/fissuring, ulceration)
Head	7			
Neck	2			
Anterior Trunk	13			
Posterior Trunk	13			
Buttocks	5			
Genitalia	1			
Upper Arms	8			
Forearms	6			
Hands	5			
Thighs	19			
Lower Leg	14			
Feet	7			
% BSA by category	100			
Severity Weighting Factor		X 1	X 2	X 4
Skin Score Subtotal				

Responses will be determined by the criteria described in the table below. Progression of disease while on treatment should be confirmed by a second assessment 1-4 weeks later so that patients who experience a temporary flare of disease due to skin infection or other intercurrent illnesses are not removed from the study prematurely.

Assessment	Description	Status
Completely clear	No evidence of disease; 100% improvement	CR
Marked Improvement	Greater than or equal to 50% decrease in skin scores compared	PR
Slight Improvement	Less than 50% decrease in skin scores compared to baseline	SD
Worse	≥ 25% increase in skin scores compared to baseline while the patient is actively taking the study drug or ≥ 50% increase in the sum of the products of the greatest diameters of pathologically positive lymph nodes (should be documented by biopsy) compared to baseline while the patent is actively taking the study drug.	PD

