# 12.1 CRITERIA FOR THERAPEUTIC RESPONSE/OUTCOME ASSESSMENT

Response and progression of disease will be evaluated in this study using a modification of the international criteria proposed by the modified Cheson criteria with incorporation of PET/CT. [Cheson B, 2007]. The imaging modality for evaluation will be dependent on disease subtype. For aggressive lymphomas (e.g. DLBCL, PTCL, HL), PET/CT will be used for evaluation of response. For indolent lymphomas, CT alone or PET/CT may be used at the discretion of the treating physician. For CTCL, please see Section 12.0.2.

Measurable disease: Measurable lesions are defined as those that can be accurately measured in at least one dimension (longest diameter to be recorded) as  $\geq$  15 mm with conventional techniques (PET, CT, MRI, x-ray). All tumor measurements must be recorded in millimeters (or decimal fractions of centimeters).

Non-measurable disease: All other lesions (or sites of disease), including small lesions (longest diameter < 15 mm), are considered non-measurable disease. Bone lesions, leptomeningeal disease, ascites, pleural/pericardial effusions, lymphoma

Memorial Sloan Kettering Cancer Center IRB Number: 14-179 A(6)
Approval date: 12-Dec-2017

Administrative Update 1 : 06-Dec-2018

cutis/pulmonis, inflammatory breast disease, abdominal masses (not followed by CT or MRI), and cystic lesions are all non-measurable.

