## Partial Remission (PR):

- Greater than or equal to 50% decrease in SPD of the six largest dominant nodes/nodal masses.
- No increase in size of other nodes, liver or spleen.
- Splenic and hepatic nodes regressed at least 50% in SPD.
- No new sites of disease.
- Bone marrow and organs other than the spleen and liver cannot be considered for evaluation for PR because involvement at these sites is considered evaluable but not measurable.

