# **Progressive Disease (PD):**

- In patients previously CR, CRUCRU, PR or SD.
- Greater than or equal to 50% increase in SPD of any previously identified abnormal node.
- Appearance of any new lesion during or at the end of therapy

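### CTCL with nodal or visceral disease: Section 12.1.1 and Appendix D define progression outside the skin differently, and no rule combines skin and extracutaneous findings into one response

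*Combined protocol and SAP*

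**What the plan says.** Section 12.1 applies modified Cheson criteria to response and progression in the study. After describing imaging for aggressive and indolent lymphomas it adds: "For CTCL, please see Section 12.0.2". That evidently means the CTCL section, headed 12.1.2, which covers skin responses by mSWAT and refers to Appendix D for detail.

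Section 12.1.1, headed as extracutaneous criteria, defines progression as "Greater than or equal to 50% increase in SPD of any previously identified abnormal node" or "Appearance of any new lesion during or at the end of therapy". Neither carries a biopsy condition. Its PR list includes "No new sites of disease".

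Appendix D, part 3, says that responses are determined by its own table. PR is "Greater than or equal to 50% decrease in skin scores compared" (the cell breaks off there, and I take the comparison to be with baseline). PD is "≥ 25% increase in skin scores compared to baseline while the patient is actively taking the study drug", or a 50% increase in the sum of the products of diameters of "pathologically positive lymph nodes (should be documented by biopsy"). The CR row asks for complete absence of disease. Above the table stands: "Progression of disease while on treatment should be confirmed by a second assessment 1-4 weeks later".

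In Appendix G, footnote 7 has imaging repeated every other cycle, if appropriate, in CTCL with known nodal or visceral disease. Footnote 9 puts response assessments after cycles 2, 5, 8, 11 and so on. Section 4.2 defines ORR by best response at any assessment. It makes progression an end of DOR and an EFS event, without saying by which criteria.

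**The concern.** In a CTCL patient with disease outside the skin, mSWAT and scans are both produced, and the two can disagree. The protocol then offers two progression rules that differ on the biopsy condition, on single node versus sum, on new lesions and on confirmation. It has no step that turns skin and extracutaneous findings into one status.

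Three secondary endpoints depend on that status. A patient with halved skin scores and a new visceral lesion is a responder if Appendix D is followed as written, and has progressed if Section 12.1.1 is followed. Because ORR takes the best response at any time, a single PR of that kind stays in the numerator. The same choice decides whether DOR starts or an EFS event occurs on that date. Without a written rule, the classification is made case by case in an open-label trial.

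**Working it through.** The plan states no figure on this point to reproduce. Efficacy is descriptive (Sections 4.2 and 14.0), and no sample size or error rate depends on these rules. The check sets the two rule sets side by side and applies both to the same patients.

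| Item | Section 12.1.1 | Appendix D table |
|---|---|---|
| Nodal PD | ≥50% increase in SPD of any abnormal node | ≥50% increase in summed products, pathologically positive nodes only |
| Biopsy | not mentioned | should document the nodes |
| New lesion | PD | not mentioned |
| Visceral disease | covered by the new-lesion rule | not mentioned in PR or PD rows |
| Skin PD | not covered | ≥25% increase in skin score, no biopsy |
| PR | ≥50% decrease in SPD and no new sites | ≥50% decrease in skin score only |
| Confirmation of PD | none stated | second assessment after 1–4 weeks |
| PD ranked above PR across compartments | not stated | not stated |

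**Illustrative patients** (all measurements are assumptions; areas in mm²)

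1. Skin score 60 to 24: (24 − 60)/60 = −60%. Abnormal node without biopsy, 600 to 960: (960 − 600)/600 = +60%. Appendix D, with the biopsy note read as a condition: PR. Section 12.1.1: PD.
2. Same skin change, nodes stable, one new visceral lesion. Appendix D: PR. Section 12.1.1: PD.
3. As patient 1, but the node is biopsy-positive. Appendix D now meets its PR row and its PD row together, with no order of precedence.
4. Two biopsy-positive nodes, 200 and 600, become 320 and 600. Single node: (320 − 200)/200 = +60%, PD under Section 12.1.1. Sum: (920 − 800)/800 = +15%, not PD under Appendix D.
5. Skin score down 30%, nodes down 60%. Appendix D: SD. Section 12.1.1: nodal PR, if its other PR conditions hold. Here Appendix D gives the less favourable result.

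**Timing.** If every other cycle is counted from cycle 2, scans fall after cycles 2, 4, 6, 8 and 10. Response assessments fall after cycles 2, 5, 8 and 11. After cycles 5 and 11 no scheduled CTCL scan coincides with the mSWAT.

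**Size.** Section 4.2 plans 10 patients per disease cohort, 20 in all. One reclassified patient moves ORR by 1/10 = 10 points in the T-cell cohort and by 1/20 = 5 points overall. With assumed counts and exact (Clopper-Pearson) 95% intervals:

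- n = 10: 4/10 = 40% (12% to 74%) against 3/10 = 30% (7% to 65%)
- n = 20: 6/20 = 30% (12% to 54%) against 5/20 = 25% (9% to 49%)

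**The case against.** The strongest reply is that the headings already divide the work: Section 12.1.1 is for extracutaneous disease and Section 12.1.2 for skin. The pointer for CTCL follows sentences about imaging modality and does not exempt CTCL from Section 12.1.1. Section 6.2 also applies Cheson criteria to CTCL without skin disease. This is a fair reading, and it makes it too strong to say that nothing indicates which section governs. It does not settle the matter, because Appendix D has a nodal progression limb of its own that differs from Section 12.1.1, and a split by compartment still needs a rule for putting the compartments together.

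A reader might infer three stronger things that the documents do not support:

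- **That Appendix D requires biopsy for any progression.** It does not: a 25% rise in skin score is PD without biopsy. The biopsy wording is a should, attached to the nodal limb only. It may refer to an earlier biopsy, so the absence of a node biopsy from the calendar proves little.
- **That Appendix D can only err towards response.** Patient 5 shows the opposite. Section 3.4 also warns that skin flare on lenalidomide may look like progression.
- **That CR is equally loose.** The CR row already demands absence of disease, and footnote 7 of Appendix G requires imaging to confirm CR in patients without nodal or visceral disease.

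It can also be said that responses are subject to central committee review (Section 16.1.2) and that efficacy has no decision threshold. Both points limit the damage. The committee would still need one written rule to apply.

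**Conclusion.** The concern holds. For CTCL with nodal or visceral disease, extracutaneous progression is defined in two incompatible ways, Appendix D scores PR on skin alone, and no overall response rule exists. The same assessment can be PR or PD, and one patient can meet both rows of Appendix D.

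The effect is modest: 10 points of ORR per reclassified patient in a cohort of 10 and 5 points in 20, with possible shifts in DOR and EFS dates. ORR changes only if the disagreement falls on a patient with no other qualifying response. The documents do not give the number of CTCL patients with extracutaneous disease, which may be small or nil. The conclusion rests on reading the table as printed and on taking the cut-off PR cell to mean a comparison with baseline. The correction should be made, but the primary safety objective does not depend on it.

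A reader might conclude that Section 12.1.1 is the right rule and that the biopsy condition should go. The documents do not support that choice. Progression also ends treatment (Section 13.2), so the sponsor must reconcile the definitions. This review does not say which should govern discontinuation.

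**What to change.** For endpoint derivation, state one overall CTCL response rule in Section 12.1.2 and Appendix D:

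- Skin is judged by mSWAT, and extracutaneous disease by a single stated definition.
- Progression in either compartment means that the patient is not counted as a responder at that assessment.
- Overall CR needs both compartments clear.
- The overall status is stated when one compartment responds and the other is stable.

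Reconcile the two nodal PD definitions on four points: the biopsy condition, any single node versus the sum, new lesions, and the 1–4 week confirmation, including which date counts as progression. State which scan is used when CTCL imaging does not fall with the response assessments, for example after cycle 5. Say in Section 4.2 or 14.0 that ORR, DOR and EFS use this overall status.

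The cost is minor rewording, with no new procedure implied by the response rule itself. Reported response rates may be slightly less favourable.
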